## 7.2.6.2 Time to Onset of Biological Response of C-peptide Following MMTT

The biological response of C-peptide is defined as a value >0.2 ng/mL for the C-peptide measurement. For Cohort 2 subjects, time to onset of biological response of C-peptide will be calculated in two ways: the time to onset of biological response from implantation, and the time to biological response within each MMTT.

For the time to onset of biological response from implantation, the time unit will be 'days' and the time itself will be calculated as:

Time to onset of biological response of C-peptide (days) = (Date of first MMTT at which the subject achieved at least one C-peptide > 0.2 ng/mL) – (Date of surgical implantation procedure for the subject) + 1

For the time to onset of biological response within each MMTT, the time unit will be 'minutes' and the time itself will be calculated as:

Time to onset of biological response of C-peptide (minutes) = (Time during MMTT at which the subject first achieved a C-peptide > 0.2 ng/mL) – (Start time of Boost Hi-Protein drink for the MMTT for the subject)

For these time-to-event analyses, subjects who did not achieve biological response will be censored. That is, for the time to onset of biological response of C peptide from implantation, subjects who did not achieve at least one C-peptide > 0.2 ng/mL during any MMTT will be censored at the time they leave the study (complete the study, or withdrawal from the study).

For the time to onset of biological response within each MMTT, subjects who did not achieve at least one C-peptide within a 4-hour MMTT will be censored at 240 minutes. Subjects who did not achieve biological response of C-peptide during a 2-hour MMTT will be censored at 120 minutes.

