 - b. Hgb <12 g/dL (males) or <11 g/dL (females).
 - c. Fasting triglycerides >500 mg/dL.
 - d. Estimated Glomerular Filtration Rate (eGFR) <60 mL/min/1.73 m2
 - e. Clinical lab value outside normal range, unless deemed as not clinically significant by the Investigator. Determination of clinical significance of a clinical lab value outside of normal range may also be evaluated by the Sponsor on a case-by-case basis.
- 21. Sustained hypertension defined as average systolic ≥160 mmHg or diastolic ≥90 mmHg at screening.
- 22. 12-lead electrocardiogram (ECG) findings demonstrating:
 - a. QT interval (QTc) >450 msec for males or >470 msec for females at screening.
 - b. Any other abnormality deemed clinically significant requiring further clinical evaluation by the Investigator.
- 23. History of unstable angina or Class 3 or 4 congestive heart failure (CHF), or any of the following conditions or procedures within the past year: stroke, myocardial infarction, life-threatening arrhythmia, major cardiovascular procedure (e.g., angioplasty, planned angioplasty, or carotid endarterectomy), or any other clinically-significant cardiovascular diagnosis or procedure.
- 24. History of coagulopathy.
- 25. Immunosuppressant therapy in the previous 30 days and/or requirements for chronic immunosuppressive therapy during the study as these may influence the expected action of the cells or graft. Individuals currently on immunosuppressant therapy may be considered on a case-by-case basis after consultation with the Sponsor.
- 26. Prescribed corticosteroid therapy above physiologic replacement doses in the previous 30 days.
- 27. Participation in a study of an investigational drug, device, or graft within five half-lives of the experimental agent or 30 days prior to enrollment in this study, whichever is longer.
- 28. Planned surgery in the general location of the implanted units at any time during study participation.
- 29. In the opinion of the Investigator, the subject is not suitable for the trial. This includes clinically significant medical and non-medical conditions, and/or clinically-significant psychiatric disorders.

Cohort 2 Only

30. A detectable stimulated serum C-peptide at any time point during the Screening Period, defined as >0.2 ng/mL (>0.0667 nmol/L).

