The 2-hour MMTT is conducted only in Cohort 2 during Visit 7 (Week 8), Visit 8 (Week 12), Visit 9 (Week 16), Visit 10 (Week 20), and Visit 12 (Week 39). In addition to the time = 0 collection, samples for glucose and C-peptide are also collected at 30, 60, 90, and 120 minutes after the start of the Boost® meal test.

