## **Efficacy**

- Change from baseline to Weeks 8, 12, 16, 20, and 39 in C-peptide  $AUC_{0-2h}$  and change from baseline to Week 52 in C-peptide  $AUC_{0-4h}$  following an MMTT.
- Change from baseline to Weeks 16, 20, 26, 39 and 52 in average daily insulin dose.
- Time to onset of biological response of C-peptide following MMTT.
- Percent of subjects achieving a positive stimulated C-peptide (defined as > 0.2 ng/mL) after implant
- Percent of subjects who achieve a 50% reduction in average weekly exogenous insulin dose from baseline to Weeks 16, 20, 26, 39, and 52.
- Percent of subjects who achieve exogenous insulin independence; of those subjects achieving insulin independence, the percent achieving HbA1c < 7.0%.

- Percent of time spent with blood glucose values at various cut points (e.g., <54 mg/dL, ≥54 to < 70 mg/dL, ≥70 mg/dL to ≤180 mg/dL, >180 mg/dL and >250 mg/dL) as measured by each subject's CGM.
- Change from baseline to Weeks 16, 20, 26, 39 and 52 in time-in-euglycemic range (≥70 mg/dL to ≤180 mg/dL), time-in-hypoglycemic ranges (<54 mg/dL and ≥54 to <70 mg/dL), and time-in-hyperglycemic ranges (>180 mg/dL and >250 mg/dL) as measured by each subject's CGM.
- Change from baseline to Weeks 16, 20, 26, 39, and 52 in weekly frequency of hypoglycemic events;
- Change from baseline in frequency of hypoglycemic events (24-hour; daytime [start between 6a.m.-12a.m.]; nocturnal [start between 12a.m.-6a.m.]) to Weeks 16, 20, 26, 39 and 52.
- Percent of subjects free of severe hypoglycemic events between study visits starting with Week 16 (i.e., Weeks 16-20, Weeks 20-26, Weeks 26-39, Weeks 39-52/ET, and Weeks 16-52/ET).

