#### 7.2.6 Data Derivations and Transformations

## 7.2.6.1 C-peptide AUC0-4h and AUC0-2h

Cohort 2 subjects will undergo MMTTs. The area under the curve (AUC) for each MMTT is calculated by adding the areas under the curve between each pair of consecutive observations. The calculation is based on the trapezoidal rule:

$$AUC = \frac{1}{2} \sum_{i=1}^{n-1} (t_{i+1} - t_i) (y_i + y_{i+1})$$

Where there are n C-peptide measurements  $y_i$  at nominal time points  $t_i$  (i=0,...,n-1), and  $(t_i+1-t_i)$  will be measured in hours.

Specifically,

$$\begin{array}{l} AUC_{0\text{-}4h} = 0.5(y_0 + y_{0.5})/2 + 0.5(y_{0.5} + y_1)/2 + 0.5(y_1 + y_{1.5})/2 + 0.5(y_{1.5} + y_2)/2 \\ + 1(y_2 + y_3)/2 + 1(y_3 + y_4)/2 \end{array}$$

$$AUC_{0\text{-}2h} = 0.5(y_0 + y_{0.5})/2 + 0.5(y_{0.5} + y_1)/2 + 0.5(y_1 + y_{1.5})/2 + 0.5(y_{1.5} + y_2)/2$$

Two-hour MMTTs will be conducted at Visit 7/Week 8; Visit 8/Week 12; Visit 9/Week 16; Visit 10/Week 20; and Visit 12/Week 39; 4-hour MMTTs will be conducted at Screening; Visit 11/Week 26; and Visit 13/Week 52 or Early Termination. C-peptide results reported as  $\leq$ 0.1 ng/mL will be imputed as 0 for determination of the AUC0-4h and AUC0-2h.

An unscheduled MMTT time point measurement will be mapped to be a scheduled time point measurement for AUC calculation if: 1) A scheduled time point measurement is missing; and 2) The time of the unscheduled sample collection is within a 10-minute sampling window for that scheduled time point except for the last scheduled time point. Specifically, within 10 minutes after the start time of Boost Hi-Protein drink for the 0 minute time point; between 20 and 40 minutes after the 0 minute time point sampling, for the 30 minute time point; between 50 and 70 minutes after the 0 minute time point sampling, for the 60 minute time point; between 80 and 100 minutes after the 0 minute time point sampling, for the 90 minute time point; between 110 and 130 minutes after the

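### One post-implant C-peptide value above the entry cut-off counts as a response, with no confirmation or rise over baseline, so stable residual C-peptide near 0.2 ng/mL can be scored as graft function

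*SAP*

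**What the plan says.** SAP 7.2.6.2 sets the definition: "The biological response of C-peptide is defined as a value >0.2 ng/mL for the C-peptide measurement". Onset from implantation is dated to the "Date of first MMTT at which the subject achieved at least one C-peptide > 0.2 ng/mL". The censoring rule confirms that one value in one test is enough: "subjects who did not achieve at least one C-peptide > 0.2 ng/mL during any MMTT will be censored at the time they leave the study". The fasting sample is not excluded.

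The responder endpoint in SAP 4.2 uses the same cut-off: "Percent of subjects achieving a positive stimulated C-peptide (defined as > 0.2 ng/mL) after implant". SAP 7.3.7.3 analyses it by Fisher's exact test and analyses time to onset by Kaplan–Meier curves with a logrank test. Neither section gives a minimum number of samples, a repeat requirement or a comparison with baseline.

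The entry rule, exclusion criterion 30 in Protocol 4.1.2, is: "A detectable stimulated serum C-peptide at any time point during the Screening Period, defined as >0.2 ng/mL". A subject whose highest screening value is exactly 0.20 is eligible.

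SAP 7.2.6.1 sets only results of 0.1 ng/mL or less to zero for the AUC. Results between 0.1 and 0.2 are therefore reportable in eligible subjects.

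**The concern.** Entry and response share one line with no gap between them. A subject with steady residual secretion just under 0.2 ng/mL can pass screening and later have one value above the line through assay noise or day-to-day variation alone. That subject becomes a responder for both endpoints and cannot lose that status.

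There are many more chances to cross after implant than at screening, and they accumulate with time in the study. With no graft function at all, the percentage positive and the onset curve would still drift upward.

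Nothing later in the plan can separate the two sources. There is no untreated arm. In Protocol 6.13 the Week 52 meal test comes before the final explant, and the Week 53 visit in Protocol 6.14 has no meal test. Loss of C-peptide after explant therefore cannot be used to show where it came from.

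**Working it through.** **The plan's own figure.** The Protocol Summary says that a detection level of 0.20 ng/mL corresponds to a 4-hour AUC of 0.8 ng × hour/mL. The trapezoidal rule in SAP 7.2.6.1 on a flat 0.2 curve gives 4 × 0.5 × 0.2 + 2 × 1 × 0.2 = 0.4 + 0.4 = 0.8. The figure reproduces.

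**Chances to cross.**
- SAP 7.2.6.1: "Two-hour MMTTs will be conducted at Visit 7/Week 8; Visit 8/Week 12; Visit 9/Week 16; Visit 10/Week 20; and Visit 12/Week 39", which is 5 tests. Protocol 7.2.2: besides time 0, "samples for glucose and C-peptide are also collected at 30, 60, 90, and 120 minutes", which makes 5 values per test.
- The 4-hour tests after implant are at Weeks 26 and 52, with 7 values each (Protocol 7.2.1).
- Scheduled post-implant values: 5 × 5 + 2 × 7 = 39. Without the seven time-0 values: 39 − 7 = 32. The lower count applies to the percent-positive endpoint if stimulated is read as post-meal; the SAP does not say.
- Stimulated screening values: 1 (oral glucose challenge) + 6 (baseline meal test) = 7.
- Unplanned meal tests (Protocol 6.15) can add values, and early termination removes some.

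**Simple illustration with independent values.** If each value has probability q of exceeding 0.2 without a graft, P(at least one) = 1 − (1 − q)^n. For q = 0.01 this is 1 − 0.99^39 = 32% for 39 values and 1 − 0.99^32 = 28% for 32. The chance of passing screening is 0.99^7 = 93%.

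**Correlated simulation.** This used 40,000 subjects per setting, constant endogenous C-peptide, no graft, log-normal variation between and within tests, and results conditional on passing screening. The residual level, both SDs and the curve shapes are assumptions; the documents give none of them. The flat shape has every post-meal value at the stated level. The peaked shape has 0.8, 0.95, 1, 0.95, 0.8 and 0.7 of peak at 30 to 240 minutes.

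| Log-SD between / within | Curve | Ever positive, peak 0.14 | Ever positive, peak 0.16 |
|---|---|---|---|
| 0.10 / 0.05 | peaked | 1% | 18% |
| 0.10 / 0.05 | flat | 2% | 33% |
| 0.15 / 0.08 | peaked | 16% | 62% |
| 0.15 / 0.08 | flat | 28% | 79% |

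At a peak of 0.10 the rate is 0.1% or less in these settings. Screening does not remove most of these subjects: with SDs 0.15 / 0.08 and a flat curve, about 93% pass at 0.14 and 70% at 0.16. Counting or omitting fasting values makes no difference here, because the fasting level is set well below the meal level.

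**Drift over time.** With a flat curve, peak 0.15 and SDs 0.15 / 0.08, the cumulative false response is about 10% at Week 8, 35% at Week 20 and 55% at Week 52.

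**What a stricter rule does.** For peaks of 0.14 and 0.16 (flat, SDs 0.15 / 0.08), two post-meal values above 0.2 in each of two consecutive tests cuts 28% and 79% to about 0.2% and 6.5%. At 0.18 it still leaves about 40%, so repetition alone is not enough. A margin closes that gap. In a related run at 0.18 (flat, SDs 0.15 / 0.10), one value above 0.2 in two consecutive tests gave 78%. Also requiring a rise of 0.1 ng/mL over the subject's baseline maximum gave 1.3%. The 0.1 is only an example.

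**The case against.** The strongest reply is that these are secondary endpoints in a Phase 1/2 trial that tests no hypotheses and treats the secondary p-values as descriptive. The primary endpoint is change in AUC with baseline as a covariate, and insulin dose and explant histology give separate evidence. All of that stands, and it limits the point's weight. It does not make the response percentage or the onset curve specific to graft function, and both will be read as absolute figures.

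A second reply is that 0.2 ng/mL may be the detection limit, so that crossing it means going from undetectable to detectable. The Protocol Summary says this only conditionally, and SAP 7.2.6.1 handles results at 0.1. Ultrasensitive samples are drawn and all data are listed, so a reader could look up baseline values, but no analysis uses them for this purpose.

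Three stronger readings are tempting:
- A reader might infer that the trial's main yes/no evidence of graft function is unsound. The documents do not give these endpoints that role.
- A reader might infer that entry enriches for subjects just under the line. Entry only removes those seen above it.
- A reader might infer that the comparison between treatment groups is biased. False responses can arise in every group, so the distortion is chiefly in absolute rates and onset times.

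**Conclusion.** The point holds as a weakness of two secondary endpoints: percent positive and time to onset. The definition lacks confirmation, a baseline comparison and any margin from the entry rule, and the design offers no later check on the source of the C-peptide.

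For an individual subject the false-response risk depends sharply on residual level: about 1–28% at a true peak of 0.14 ng/mL and 18–79% at 0.16, over the assumed variation and curve shapes, and negligible at 0.10. These are conditional on assumptions, not estimates for the trial. The documents give neither assay variation nor the distribution of residual C-peptide, so the inflation of the Cohort 2 response percentage cannot be computed and could be small.

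**What to change.** Keep the single-value definition as the protocol endpoint. In SAP 7.2.6.2 and 7.3.7.3, add a prespecified confirmed-response analysis, reported beside it for both percent positive and time to onset.

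Confirmed response means at least two post-meal values in one meal test that are above 0.2 ng/mL and exceed the subject's own baseline meal-test peak by a margin, repeated at the next meal test. Onset is dated to the first of the two tests. Fix the margin in advance from assay and within-subject variation. Show each responder's baseline peak.

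The cost is SAP text and two further outputs from data already collected. Replacing the endpoint would be a larger step, because Protocol Section 10 requires an amendment for major endpoint changes; adding an analysis beside it leaves the endpoint as it is. The drawback is that transient responses, and those first seen at the last meal test (Week 52, or the last before an early explant), cannot be confirmed and must be reported as unconfirmed.

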7.2. Mixed Meal Tolerance Test (MMTT) – Cohort 2 only

MMTTs are conducted after all other vital signs evaluations and laboratory tests have been collected. The MMTT test should only be started if the subject has been fasting for at least eight (8) hours. The MMTT may be rescheduled within the visit window if needed. All MMTT supplies will be provided by the Sponsor or designee. Basal exogenous insulin will be continued during the test, but any short-acting insulin will be withheld starting four hours prior to starting the test. Prior to initiating the MMTT, the subject's fasting glucose will be tested at the site and the value must be within 70-200 mg/dL to begin the MMTT. If the fasting glucose is not initially within range, the site may recheck levels while the subject is still at the clinic. If the fasting glucose remains outside of the allowed range, the subject must return to the site within the visit window and attempt the MMTT again.

An intravenous catheter can be placed in a patent vein in the subject's arm for the collection of blood samples. Insertion of the catheter should occur at least 30 minutes prior to any blood collections on the days MMTTs are performed. The subject should sit upright during the test. Slow walking is permitted, but vigorous exercise should be avoided.

Baseline, fasting blood samples are drawn for glucose and C-peptide within approximately five minutes prior to the start of the meal test. At time = 0, the subject drinks Boost® Hi-Protein (volume equal to 6 mL/kg body weight to a maximum of 360 mL). The entire drink must be ingested within 15 minutes.

For any visits requiring both an MMTT and an explant procedure, it is acceptable to perform the MMTT on a separate day up to 5 days prior to the explant procedure. Further details regarding MMTTs may be outlined in the study reference manual.

7.2.1. 4-Hour Mixed Meal Tolerance Test – Cohort 2 Only

The 4-hour MMTT is conducted only in Cohort 2 during Visit 2 (Week -4), Visit 11 (Week 26), and Visit 13 (Week 52 / Completion or ET). In addition to the time = 0 collection, samples for glucose and C-peptide are also collected at 30, 60, 90, 120, 180, and 240 minutes after the start of the Boost® meal test.

7.2.2. 2-Hour Mixed Meal Tolerance Test – Cohort 2 Only

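### SAP 7.2.6.2 gives a zero or negative within-MMTT response time to a subject already above 0.2 ng/mL before the meal, and no rule says how to handle it

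*SAP*

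**What the plan says.** SAP 7.2.6.2 sets the threshold without excluding any sample: "The biological response of C-peptide is defined as a value >0.2 ng/mL for the C-peptide measurement". It then defines two times.

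- **Within each MMTT, in minutes:** the "Time during MMTT at which the subject first achieved a C-peptide > 0.2 ng/mL" minus the "Start time of Boost Hi-Protein drink for the MMTT for the subject". Non-responders are censored at 120 minutes (2-hour test) or 240 minutes (4-hour test).
- **From implantation, in days:** the date of the first MMTT with at least one value above 0.2 ng/mL, minus the implant date, plus 1. Subjects with no such value at any MMTT "will be censored at the time they leave the study".

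Protocol 7.2 fixes the sampling order: "Baseline, fasting blood samples are drawn for glucose and C-peptide within approximately five minutes prior to the start of the meal test". Then, "At time = 0, the subject drinks" the test meal.

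SAP 7.2.6.1 places C-peptide measurements "at nominal time points", but for the AUC. Its window for mapping an unscheduled sample is "within 10 minutes after the start time of Boost Hi-Protein drink for the 0 minute time point", also for the AUC.

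SAP 7.3.7.3 analyses time to onset by Kaplan-Meier and log-rank and treats secondary p-values as descriptive.

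**The concern.** The formula takes its origin from the drink, while the first sample that can meet the threshold is drawn before the drink. For a subject who is above 0.2 ng/mL at fasting, the event comes before or at the origin. The SAP gives a censoring rule for subjects who never respond, but none for a response time of zero or less.

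Such a result is plausible. Exclusion criterion 30 removes Cohort 2 candidates whose stimulated C-peptide exceeds 0.2 ng/mL at screening, so a fasting value above that level after implantation points to graft output. If a program discards the record, a responder leaves both the event count and the risk set of that treatment group. The choice would then be made at programming, in an open-label study, and not in the plan.

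The same section has a smaller problem. In the from-implant analysis a response can be seen only at an MMTT, yet non-responders stay in the risk set until they leave the study. Time after the last MMTT then counts as response-free although no response could have been observed.

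**Working it through.** The documents state no event rate, power or sample size for this endpoint, so there is no figure to reproduce.

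**1. Time given to a fasting responder.** Let S be the drink start and d the minutes by which the fasting draw precedes it. Protocol 7.2 gives d of about 0 to 5. The SAP formula gives

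T = (S - d) - S = -d, so T lies between about -5 and 0 minutes.

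On clock times T is negative whenever the draw comes before the drink. If the pre-meal sample carries its nominal time of 0, T = 0.

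**2. Search for a rule that covers it.**

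- SAP 7.2.6.2: the censoring text covers non-responders only.
- SAP 7.2.6.1: nominal times are stated for the AUC. The 0-minute window covers unscheduled samples from 0 to 10 minutes after drink start, so it does not reach a pre-meal draw.
- Protocol 7.2: the draw comes before the drink, and the protocol labels that collection as time 0.
- SAP 7.3.7.3: the method is named, without software or any handling of T ≤ 0.

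**3. What the handling could do (assumed data).** Take 20 subjects in a high-dose and 20 in a low-dose group. Post-meal responses fall at 30 to 120 minutes, non-responders are censored at 240 minutes, and the low group has 4 responders, all post-meal. Log-rank results:

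| High group, pre-meal + post-meal responders | Pre-meal kept as events at 0 | p | Pre-meal dropped | p |
|---|---|---|---|---|
| 2 + 6 | 8/20 vs 4/20 | 0.144 | 6/18 vs 4/20 | 0.340 |
| 4 + 6 | 10/20 vs 4/20 | 0.034 | 6/16 vs 4/20 | 0.234 |
| 8 + 4 | 12/20 vs 4/20 | 0.006 | 4/12 vs 4/20 | 0.405 |

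The statsmodels survival estimator accepted a negative time. Log-rank with these events left ahead of time 0 gave the same p-values as setting them to 0, because the test uses only the order of times and all pre-meal events shared one time in these data. The result therefore turns on whether the records are kept or dropped.

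**4. Late censoring in the from-implant analysis.** From the target days in SAP 7.2.2:

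- Completer: last MMTT at Day 365, follow-up at Day 372; 372 - 365 = 7 days.
- Subject lost just before Week 39 or Week 52 without an early-termination MMTT: 274 - 183 = 91 days, or 365 - 274 = 91 days; 91/7 = 13 weeks.

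These subjects stay in the denominator for events dated in the gap, which makes the estimated response probability slightly too low.

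**The case against.** Several points on the other side stand.

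- **Nominal time is a fair reading.** The protocol labels the pre-meal collection as time 0, the AUC uses nominal times, and within-test censoring is at 120 or 240 minutes. On that reading T is 0, not negative. Subtracting a subject-specific drink start does suggest clock times, so the text leaves this open.
- **Loss of subjects is not certain.** It depends on the software or program, and the documents name neither. Step 3 shows that negative times can be kept without harm.
- **The pre-meal sample may not be a response to the meal.** The endpoint is onset following an MMTT. If the sponsor excludes that sample, the first eligible one is at 30 minutes and the non-positive time does not arise. The SAP does not take that decision.
- **The reach is narrow.** The from-implant version counts a fasting responder as an event, and neither the percent with positive stimulated C-peptide nor the primary AUC uses this time. No hypotheses are tested, and all data are listed.
- **The censoring effect is small.** The early-termination visit includes a 4-hour MMTT, so the longer gap needs a subject who leaves without one.

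These points limit the consequence. They do not supply the missing rule, and a data listing does not repair a curve from which responders were dropped.

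**Conclusion.** The point holds as a gap in the definition. As written, SAP 7.2.6.2 gives a fasting responder a time of about -5 to 0 minutes and says nothing about its handling. The within-MMTT Kaplan-Meier and log-rank analysis can therefore vary with the software or the programmer. The size cannot be estimated, because the documents give no rate of fasting values above 0.2 ng/mL; the p-values in the table rest on assumed data and show only that keeping or dropping the records can matter.

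A reader might infer that the trial will lose its strongest graft responders and so be biased against its best dose. The documents do not support that. They state no exclusion of negative times and do not rank graft function by fasting C-peptide. The exposure is confined to one of two versions of a secondary endpoint with descriptive p-values.

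The from-implant censoring point also holds, with small effect: about 7 days for completers, and up to about 13 weeks for a subject lost after Week 26 without an early-termination MMTT, assuming scheduled visits fall on target days and no earlier MMTT was missed.

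**What to change.** In SAP 7.2.6.2:

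1. State that within-MMTT times are nominal, with the pre-meal sample at time 0.
2. Count a pre-meal value above 0.2 ng/mL as an event at 0, and tabulate these fasting responders by treatment group and visit.
3. If the sponsor decides that the pre-meal sample is not a response to the meal, say so and report those subjects separately, so that none leaves the analysis through a negative time.
4. In the from-implant analysis, censor non-responders at the date of the last evaluable post-implant MMTT, or at Day 1 if there is none.

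The cost is a few sentences in the SAP and the matching program code. No new data are needed. The text should be settled before the results are seen.
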